5.4 AEs coding/grading

Adverse events (AEs) are to be coded with the MedDRA dictionary based on the latest version available at the time of the analyses (version 24 or above) gives preferred term (PT) and primary system organ class (SOC) information. AEs will be graded using the common toxicity criteria for adverse events (CTCAE) version 5.0.

5.5 Laboratory parameters derivations

[Table 5.5-1](#) shows the criteria for clinically notable laboratory values and includes the direction of interest when analyzing worst case values in form of maximum and/or minimum post-baseline values.

Not all parameters have notable criteria defined.

If the direction of interest is given as "High" the maximum value will be calculated and used as worst value, if the direction is given as "Low" the minimum value will be taken, and if it is given as "Low and high", both the minimum value and the maximum value will be calculated and presented in summary tables.

Table 5.5-1 Clinical notable criteria for selected laboratory tests

Laboratory parameter (unit)	Lower bound of clinically notable range	Upper bound of clinically notable range	Direction of interest for worst case value
A. Hematology			
Hematocrit (v/v)			
Male	0.37		Low
Female	0.32		Low
Hemoglobin (g/L)			
Male	115		Low
Female	95		Low
Erythrocytes			Low
WBC (x10E9/L)	2.8	16.0	Low and High
Basophils	-		High
Eosinophils	-		High
Lymphocytes (x10E9/L)	0.5	4	Low and High
Monocytes	-		High
Neutrophils (x10E9/L)	1.5	10	Low and High
Platelets (x10E9/L)	75	700	Low and High
B. Chemistry			
Albumin (g/L)	25	-	Low
Alkaline Phosphatase (U/L)	-	3xULN	High
ALT/SGPT (U/L)	-	3xULN	High
AST/SGOT (U/L)	-	3xULN	High
Bilirubin Total (mmol/L)	-	34.2	High
Direct bilirubin	-		High
BUN (mmol/L)	-	10.7	High
Creatinine (umol/L)	-	177	High
Creatinine kinase	-	3 x ULN	High
Gamma GT (U/L)	-	3 x ULN	High
Bicarbonate			Low and High
Chloride	90	115	Low and High
Potassium (mmol/L)	3	5.5	Low and High
Magnesium (mmol/L)	0.51	1.07	Low and High
Calcium	1.75	3.0	Low and High
LDH	-		High
Phosphorus	0.6	1.6	Low and High
Sodium (mmol/L)	130	150	Low and High
C-Reactive Protein (CRP) (mg/L)	-	100	High

Laboratory parameter (unit)	Lower bound of clinically notable range	Upper bound of clinically notable range	Direction of interest for worst case value
Fibrinogen	-		High
Total protein (g/L)	45	-	Low
Uric Acid			
Male	-	595	High
Female	-	476	High
Amylase	-	1.5 x ULN	High
Lipase	-	1.5 x ULN	High
Glucose (mmol/L)	3.0	11	Low and High
D-dimer	-	3 x ULN	High
Ferritin (ng/mL)		3 x ULN	High
C. Coagulation			
PT		-	Low
INR		1.5 x ULN	High
APTT		1.5 x ULN	High

v = volume, ULN = upper limit of normal

Table 5.5-2 shows the criteria for clinically notable liver test values.

When a criterion contains multiple laboratory parameters, the criterion will only be considered to have been met when all conditions occur within a 3-day window. A case where all criteria are met at a post-baseline time point will be considered as newly occurring if the criteria are not met at baseline and will be considered as worsening if the criteria are met at baseline and at least one component is worsening from baseline irrespective of whether the other(s) are better.

Table 5.5-2 Notable liver function test values

Criterion
ALT > 3 x the upper limit of normal range (ULN)
ALT > 5 x ULN
ALT > 8 x ULN
ALT > 10 x ULN
ALT > 20 x ULN
ALT or AST > 3 x ULN
ALT or AST > 5 x ULN
ALT or AST > 8 x ULN
ALT or AST > 10 x ULN
ALT or AST > 20 x ULN
Total bilirubin > 1 x ULN
Total bilirubin > 1.5 x ULN
Total bilirubin > 2 x ULN
Total bilirubin > 3 x ULN
ALP > 1.5 x ULN
ALP > 2 x ULN
ALP > 3 x ULN
ALP > 5 x ULN
ALT or AST > 3 x ULN and total bilirubin > 1.5 x ULN
ALT or AST > 3 x ULN and total bilirubin > 2 x ULN
ALT or AST > 5 x ULN and total bilirubin > 2 x ULN
ALT or AST > 8 x ULN and total bilirubin > 2 x ULN
ALT or AST > 10 x ULN and total bilirubin > 2 x ULN
ALT or AST > 20 x ULN and total bilirubin > 2 x ULN
ALT > 3 x ULN and total bilirubin > 2 x ULN
ALP > 5 x ULN and total bilirubin > 2 x ULN
ALT or AST > 3 x ULN and Total Bilirubin > 2 x ULN and ALP < 2 x ULN (Hy's law)

ALT = alanine aminotransferase, AST = aspartate aminotransferase, ALP = alkaline phosphatase

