#### **8.4.1 Laboratory evaluations**

Clinically significant abnormalities must be recorded as either medical history/current medical conditions or adverse events as appropriate.

In all cases, the investigator must document in the source documents the clinical considerations (i.e., result was/was not clinically significant and/or medically relevant) in allowing or disallowing the patient to continue in the study.

A central laboratory will be used for analysis of all safety specimens collected. Details on the collection, shipment of samples and reporting of results by the central laboratory are provided to investigators in the central laboratory manual.

All abnormal lab results must be evaluated for criteria defining an AE and reported as such if the criteria are met. For those lab AEs, repeated evaluations are mandatory until normalization of the result(s) or until the result is no longer considered to be clinically significant.

Test category	Test name
Hematology	Hematocrit, Hemoglobin, Platelets, Red blood cells, White blood cells, Differential (Basophils, Eosinophils, Lymphocytes, Monocytes, Neutrophils, Other)
Chemistry	Albumin, Alkaline phosphatase, alanine aminotransferase (ALT), aspartate aminotransferase (AST), Gamma-glutamyl-transferase (GGT), Lactate dehydrogenase (LDH), Bicarbonate, Calcium, Magnesium, Phosphorus, Chloride, Sodium, Potassium, Creatinine, Creatine kinase, Direct Bilirubin, Total Bilirubin, Total Protein, Blood Urea Nitrogen (BUN) or Urea, Uric Acid, Amylase, Lipase, Glucose (non-fasting), C-reactive protein (CRP), D-Dimer, Ferritin
Coagulation	Prothrombin time (PT), International normalized ratio (INR), Activated partial thromboplastin time (APTT)
Pregnancy Test	Serum / Urine pregnancy test

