2.8.3 Laboratory data

Laboratory data include measurements of all parameters below:

Test Category	Test Name
Hematology	Hematocrit, Hemoglobin, Platelets, Red blood cells, White blood cells, Differential (Basophils, Eosinophils, Lymphocytes, Monocytes, Neutrophils, Other)
Chemistry	Albumin, Alkaline phosphatase, ALT, AST, Gamma-glutamyl-transferase (GGT), Lactate dehydrogenase (LDH), Bicarbonate, Calcium, Magnesium, Phosphorus, Chloride, Sodium, Potassium, Creatinine, Creatine kinase, Direct Bilirubin, Total Bilirubin, Total Protein, Blood Urea Nitrogen (BUN) or Urea, Uric Acid, Amylase, Lipase, Glucose (non-fasting), CRP, D-Dimer, Ferritin
Coagulation	Prothrombin time (PT), International normalized ratio [INR], Activated partial thromboplastin time (APTT)
Pregnancy Test	Serum / Urine pregnancy test

Clinically notable abnormalities and abnormalities in liver function tests (LFT) are described in [Section 5.5](#).

Absolute values and change from baseline will be summarized for continuous laboratory parameters by treatment and scheduled visit, including the worst post-baseline value. The direction of interest for worst post-baseline value for selected hematology and biochemistry parameters is shown in [Section 5.4](#).

For selected laboratory tests, the number and percentage of patients with newly occurring or worsening laboratory abnormalities meeting the clinically notable criteria at any time post-

baseline, considering all post-baseline data from scheduled, unscheduled and premature discontinuation visits, will be summarized by treatment and laboratory parameter.

Furthermore, the number and percentage of patients with newly occurring or worsening abnormalities in liver function tests (LFT) will be summarized by treatment and at any time post-baseline considering all post-baseline data from scheduled, unscheduled and premature discontinuation visit.

The number (%) of patients with newly occurring or worsening of notable laboratory values will be provided.

Shift tables using the low/normal/high/ (low and high) classification will be used to compare baseline to the worst post-baseline value.

Listing of all laboratory data of patients with notable abnormal laboratory values will be provided with the classifications relative to the laboratory normal ranges.

Urine pregnancy test data will be summarized using frequency and percentage by treatment. A listing of all pregnancy test data will be provided.

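### SAP Table 5.5-1 sets the worst direction for prothrombin time (PT) to 'Low', opposite to INR and APTT, and gives no unit; if PT is in seconds, its worst-value summary takes each patient's shortest time

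*SAP*

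**What the plan says.** SAP 5.5 converts each parameter's direction of interest into a worst value. 'High' takes the maximum, 'Low and high' takes both extremes, and "if the direction is given as 'Low' the minimum value will be taken".

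In part C (Coagulation) of Table 5.5-1, PT has a blank lower bound, a dash for the upper bound, no unit and the direction 'Low'. The next two rows read "INR 1.5 x ULN High" and "APTT 1.5 x ULN High".

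SAP 2.8.3 uses the worst value in two outputs:

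- Summaries: "Absolute values and change from baseline will be summarized for continuous laboratory parameters by treatment and scheduled visit, including the worst post-baseline value".
- Shift tables: "Shift tables using the low/normal/high/ (low and high) classification will be used to compare baseline to the worst post-baseline value".

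The same section states the scope of the directions: "The direction of interest for worst post-baseline value for selected hematology and biochemistry parameters is shown in" Section 5.4. The table is in fact in Section 5.5, and it also covers coagulation.

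SAP 2.8.3 and Protocol 8.4.1 both list the test as prothrombin time. Neither gives a unit.

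**The concern.** INR is a standardized form of the prothrombin time measured on the same sample. If PT is a time, the two rise together, so the worst PT cannot be the lowest while the worst INR is the highest. The protocol pairs the two as PT/INR in Section 10.2.1 and Table 16-3, and its liver tables (16-1 and 16-2) treat an INR above 1.5 as the signal.

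Clinical laboratory measurements are a secondary safety endpoint in both Parts. Worst-value summaries exist to catch extremes that visit-by-visit statistics dilute. For a PT in seconds, the summary would keep the opposite extreme. Anticoagulants are permitted (Protocol 6.2.1), so prolonged values are plausible in this population and should be displayed correctly by arm.

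**Working it through.** The documents contain no figure to reproduce. The check sets the provisions side by side and applies the rule to assumed values.

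**Step 1. Inputs.**

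| Parameter | Lower bound | Upper bound | Direction | Worst value under SAP 5.5 |
|---|---|---|---|---|
| PT | blank | dash | Low | minimum |
| INR | blank | 1.5 x ULN | High | maximum |
| APTT | blank | 1.5 x ULN | High | maximum |

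Protocol Table 8-1 schedules five post-baseline coagulation draws in Part A: Days 3, 15, 29, 61 and 91.

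**Step 2. A prolongation at a scheduled visit, PT in seconds.** Assume a normal range of 11 to 14 s, a normal baseline, and post-baseline values of 12, 19, 12, 12, 12 s.

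- Direction 'Low': min(12, 19, 12, 12, 12) = 12 s, classed as normal.
- Direction 'High': max(12, 19, 12, 12, 12) = 19 s, classed as high.

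The PT worst-value row shows 12 s. A shift table built literally on that value shows normal to normal. The 19 s value still enters the summary for its own visit, and SAP 2.1 includes the maximum among the statistics for continuous variables.

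**Step 3. A prolongation at an unscheduled visit.** Assume post-baseline values of 12, 18, 13 s with the same range, where 18 s is an unscheduled draw. SAP 2.8.3 summarizes by scheduled visit, and SAP 2.1.1.6 brings unscheduled laboratory values in through the worst post-baseline summaries. Under 'Low' the worst value is min(12, 18, 13) = 12 s. The 18 s value then appears in neither the by-visit PT summary nor the PT worst-value row.

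**Step 4. Can another PT output catch it?** The notable-value counts do use unscheduled visits, but PT has no bound in either direction, so no PT value can be counted as notable or trigger the listing of patients with notable values.

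**Step 5. Can INR or APTT catch it?** Yes, where they were measured and raised. Their worst value is the maximum, and both have a limit of 1.5 x ULN. A patient notable on either has all laboratory data listed, which would include PT.

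**Step 6. The other unit.** If PT is reported as percent activity, impaired clotting lowers the value while raising INR. 'Low' for PT and 'High' for INR then agree, and the table is right apart from its label.

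**The case against.** The strongest objection is that the row may not be an error. It has no unit, and reporting details are left to a laboratory manual outside these documents (Protocol 8.4.1). The dash and the direction also agree with each other. Elsewhere in the table a dash usually marks the side of no interest: Albumin and Total protein have a dash for the upper bound and 'Low', while LDH and Basophils have a dash for the lower bound and 'High'. PT, with a dash for the upper bound and 'Low', fits the pattern of a test that is adverse when low. This stands: percent activity cannot be excluded, and switching to 'High' without checking the unit could create the reversal it is meant to remove. The test's name and its pairing with INR favor a time but do not settle the scale.

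Three stronger readings are tempting, and the documents do not support them.

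- *The plan hides prolonged PT.* By-visit PT summaries include the maximum, INR and APTT run in the 'High' direction, and clinically significant results become adverse events (Protocol 8.4.1 and 10.1.1). The gap is in the PT worst-value output.
- *A patient with one normal PT can never be shown as shifted to high.* The shift classification has a combined 'low and high' class, which can be filled only if both extremes are considered. A programmer could therefore classify PT on both. The text nevertheless ties the table to the worst value, which for PT is the minimum, so the restrictive reading is the literal one but not the only one.
- *The PT and INR tables would contradict each other.* They would show different extremes under stated directions, which is confusing but not a contradiction in the data.

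**Conclusion.** The concern holds in conditional form. If PT is reported in seconds, the worst post-baseline PT summary is reversed as written, and on a literal reading so is the PT shift table. The output that would otherwise lose a prolonged value altogether is the PT summary for an unscheduled draw, because the by-visit tables do not carry it and PT has no notable bound. If PT is reported as percent activity, the direction is right and the defect is a missing unit.

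The size is small. It concerns one parameter in descriptive safety tables. The primary analysis, the INR-based liver rules and the study stopping rules do not use this direction. The number of affected patients cannot be estimated from the documents, and the series above are illustrations with assumed values and an assumed normal range. The row needs an edit under either unit. The wrong section number and the omission of coagulation in SAP 2.8.3 are separate slips that do not depend on the unit.

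**What to change.** 1. Confirm with the central laboratory how PT is reported, and put the unit in Table 5.5-1.
2. If seconds: change the PT direction to 'High', matching INR and APTT, and adjust the dash in the upper-bound cell so that the row is consistent.
3. If percent activity: keep 'Low' and label the row PT activity (%).
4. In SAP 2.8.3, change the cross-reference for the directions from Section 5.4 to Section 5.5, and add coagulation to the parameter groups it names.

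The cost is one query to the laboratory, one or two table cells, one sentence in SAP 2.8.3 and, if the unit is seconds, one line of programming. No new data are needed. SAP Section 1 already plans an amendment before the first Part B patient, so the correction should at the latest be made there.

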#### **10.1.4 AEs of Special Interest**

The following events are AEs of Special Interest (AESI) for this study:

- A CTCAE Grade 2 or higher (i.e. requiring intervention) of:
  - Infusion site reactions
  - Hypersensitivity reactions (including anaphylaxis, immune complex mediated hypersensitivity, cytokine release syndrome and other hypersensitivity reactions)
- Worsening of COVID-19 disease that is reported as a moderate or severe AE per investigator judgment, with onset within 1 week of study drug administration.
- Liver events requiring follow-up (see [Appendix 16.3](#))
- Renal events requiring follow-up (see [Appendix 16.4](#))

The reporting of AESIs, even if non-serious, follows the same procedures and timelines as the reporting of SAEs: They must be reported to the medical monitor safety desk within 24 hours of learning of their occurrence, using the same forms.

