### 10.2.2 Renal safety monitoring

Once a patient is exposed to study treatment, the following abnormal renal laboratory alert value should be assessed during the study period:

- Serum creatinine increase  $\geq 25\%$  compared to baseline during normal hydration status  
Abnormal renal event findings must be confirmed within 24 to 48 hours after the first assessment.

Once a patient is exposed to study treatment, renal laboratory alerts or renal safety events should be monitored and followed up by the investigator or designated trial staff as summarized in [Table 16-4](#).

Every renal laboratory trigger or renal event as defined in [Table 16-4](#) should be followed up by the investigator or designated personnel at the trial site as summarized in [Table 16-4](#).

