## 16.4 Appendix 4: Specific renal alert criteria and actions and event follow-up

**Table 16-4 Specific renal alert criteria and actions**

Serum Event	
Serum creatinine increase 25% – 49% compared to baseline, exceeding the normal range and/or considered clinically significant	Confirm 25% increase after 24-48 hours Follow-up within 2-5 days
Acute Kidney Injury: Serum creatinine increase $\geq 50\%$ compared to baseline	Follow-up within 24-48 hours if possible Consider participant hospitalization /specialized treatment
For all renal events:	
Document contributing factors in the CRF: co-medication, other co-morbid conditions, and additional diagnostic procedures performed	
Monitor participant regularly (frequency at investigator's discretion) until either:	
Event resolution: sCr within 10% of baseline or protein-creatinine ratio within 50% of baseline, or	
Event stabilization: sCr level with $\pm 10\%$ variability over last 6 months or protein-creatinine ratio stabilization at a new level with $\pm 50\%$ variability over last 6 months.	

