2.8.1.1 Adverse events of special interest / grouping of AEs

The following events are AEs of Special Interest (AESI) for this study:

- A CTCAE grade 2 or higher (i.e. requiring intervention) of: Infusion site reactions;
- Hypersensitivity reactions (including anaphylaxis, immune complex mediated hypersensitivity, cytokine release syndrome and other hypersensitivity reactions)
- Worsening of COVID-19 disease that is reported as a moderate or severe AE per investigator judgement, with onset within 1 week of study drug administration.
- Liver events requiring follow-up
- Renal events requiring follow-up

The number (and percentage) of patients with each of the AESIs will be summarized for each Part

- by treatment;
- by treatment and maximum CTCAE grade; and,
- and by treatment, primary system organ class, and preferred term.

A listing of AESIs will be provided. AESIs will be analyzed as flagged by the investigator on the eCRF.

Safety topics of interest are defined in the electronic case retrieval sheet (eCRS). These will be summarized for each part

- by safety topic of interest
- by safety topic of interest and preferred term
- by safety topic of interest and preferred term for those AEs marked as AESI by the investigator

AESIs and safety topics of interest will be in addition will be summarized for each treatment-emergent Anti-Drug Antibodies (TE-ADA) status. ADA data will only be partially available at the time of part A primary analysis, therefore this analysis will only be done at the time of final lock i.e., day 91 analyses.

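### The SAP flags creatinine only against a fixed 177 umol/L, so no programmed table counts patients who meet the protocol's baseline-relative renal criteria

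*SAP*

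**What the plan says.** SAP Section 5.5, Table 5.5-1, sets the limits for notable laboratory values. The row "Creatinine (umol/L" has no lower limit, an upper limit of 177 and direction High. It has no criterion based on change from baseline. SAP Section 2.8.3 counts patients by arm with "newly occurring or worsening laboratory abnormalities meeting the clinically notable criteria" and lists the laboratory data of patients who have a notable value. For creatinine, both outputs turn on 177 umol/L.

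The protocol measures the renal signal against the patient's own baseline. Section 10.2.2 sets an alert at a rise of 25% or more "compared to baseline during normal hydration status" and asks for confirmation within 24 to 48 hours. Table 16-4 has two tiers. The lower is a 25% to 49% rise with the added condition "exceeding the normal range and/or considered clinically significant". The upper, "Acute Kidney Injury: Serum creatinine increase", begins at 50%.

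Renal events also have an adverse-event route. Protocol Section 10.1.4 names "Renal events requiring follow-up (see" Appendix 16.4) as an AESI. SAP Section 2.8.1.1 repeats "Renal events requiring follow-up" and tabulates AESIs by arm, by maximum CTCAE grade, and by organ class and preferred term, with a listing. It adds: "AESIs will be analyzed as flagged by the investigator on the eCRF".

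SAP Section 2.8.3 plans two further outputs that cover creatinine and do not use 177: summaries of values and changes from baseline by arm and visit, including the worst post-baseline value, and low/normal/high shift tables from baseline to the worst value.

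**The concern.** The laboratory tables and the protocol use different yardsticks for the same signal. A fixed limit suits patients whose creatinine starts high. It is insensitive in patients who start low, in whom a large proportional rise can stay under the limit.

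Renal events are a named AESI. The rationale of Global Amendment 1 says that renal reporting and creatinine follow-up testing were adjusted for patients with acute COVID-19 and for concomitant drugs such as NSAIDs. AESIs, AEs and SAEs are among the stated inputs to the Part B dose (Protocol Section 12.4.2, SAP Section 2.5.2). If sites under-report renal events, nothing programmed from the laboratory data would show it. For the liver the SAP does not rely on flags alone: Table 5.5-2 programs graded criteria next to the liver AESIs.

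**Working it through.** **Inputs.** The limit of 177 umol/L is from SAP Table 5.5-1. The 25% and 50% rises are from Protocol Section 10.2.2 and Table 16-4. The documents give neither the baseline creatinine distribution nor the size of the rises, so any values used for these are assumptions. The 177 limit is stated without a derivation, so there is no planned figure to reproduce.

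**Step 1, break-even baseline.** The baseline at which a given rise just reaches the limit is 177/(1 + rise).
- 50% rise: 177/1.50 = 118.0 umol/L.
- 25% rise: 177/1.25 = 141.6 umol/L.

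Below these baselines a patient can satisfy the percentage in the protocol without reaching the SAP limit.

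**Step 2, rise needed before the SAP flags it**, from 177/baseline − 1, for assumed baselines:
- 60 umol/L: 177/60 = 2.95, a rise of 195%.
- 80 umol/L: 177/80 = 2.21, a rise of 121%.
- 100 umol/L: 177/100 = 1.77, a rise of 77%.

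**Step 3, examples.** From 80 to 120 umol/L is a 50% rise, and from 80 to 160 is a 100% rise. Both meet the protocol's upper tier and neither reaches 177.

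**Step 4, would another planned output count these patients?**
- Change-from-baseline summaries contain their values, but as means, quartiles and extremes of absolute change. They give no number of patients past a percentage.
- Shift tables show a move from normal to high. They show nothing for a rise that stays within normal, or for a patient already high at baseline, and they do not separate a marginal rise from a doubling.
- AESI tables apply the protocol's criteria, but through the investigator's flag. Under Protocol Section 10.1.1 an abnormal laboratory value is an AE only if it causes signs or symptoms, is judged clinically significant, or needs therapy. A rise that the site judges not significant may therefore go unflagged.

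**Step 5, how many would be missed?** This is illustration only. Take lognormal baselines with median 70 to 100 umol/L and coefficient of variation 20% to 40%. Among patients past the 50% line, let the fold rise be 1.5 × exp(X), with X exponential of mean 0.15, 0.3 or 0.6. The median fold rise is then about 1.66, 1.85 or 2.27. The simulated share at or below 177 (400,000 draws per setting) is:
- median fold 1.66: 52% to 93%;
- median fold 1.85: 39% to 78%;
- median fold 2.27: 24% to 56%.

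Overall the range is 24% to 93%, and it is driven by the assumptions.

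**The case against.** The strongest reply is that the protocol-defined signal is already reported. Renal events under Appendix 16.4 are AESIs, must be reported within 24 hours even if non-serious, and are tabulated by arm and listed. AESIs, and not notable-value counts, are what the dose-selection text names. An independent committee reviews safety data. SAP Section 2.8.1.1 also summarizes safety topics of interest defined in a separate retrieval sheet; that sheet is not among the documents, so whether it has a renal topic cannot be judged. Site alert criteria and SAP notable limits also serve different purposes, so a difference between them is not in itself a contradiction.

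Much of this stands. A reader might infer that the AESI table is the only other renal output, or that the laboratory tables could not show a dose-related rise. SAP Section 2.8.3 supports neither reading, since change from baseline by arm and the shift tables are both planned. The liver comparison is also only partial: Table 5.5-2 uses multiples of the upper limit of normal and omits the protocol's liver trigger of more than twice baseline.

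A bare percentage table would not reproduce the protocol's definitions exactly. The lower tier carries a normal-range or clinical-significance condition, and Section 10.2.2 adds hydration status and confirmation.

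The reply does not supply an independent check. The AESI counts rest on the flag, and no planned output sets that flag against the laboratory values. Baseline-relative criteria are not foreign to this SAP: the adult blood pressure limits in Table 5.6-1 already require a change from baseline.

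**Conclusion.** The point holds as a gap in safety reporting. A patient with baseline creatinine below 118 umol/L can meet the protocol's acute kidney injury criterion without entering the SAP's notable-value counts, and enters the listing only if another parameter is notable. For a 25% rise the corresponding baseline is 141.6 umol/L. These two figures follow from the documents alone.

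A reader might infer that most patients with acute kidney injury would be missed. The documents do not support that, because the share depends on baselines and rises that they do not give; the illustration runs from 24% to 93%. Nor would such patients be lost from safety reporting: their values enter the change-from-baseline summaries, some would appear in the shift tables, and flagged cases would appear as AESIs. What is absent is a programmed count by arm on the protocol's own criteria. The primary analysis, error rate and estimand are unaffected.

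**What to change.** In SAP Section 2.8.3 and Table 5.5-1, keep the 177 umol/L limit and add, by arm, the number and percentage of patients whose worst post-baseline creatinine is:
- 25% to 49% above baseline, also split by whether the value exceeds the normal range, to reflect the condition in Protocol Table 16-4;
- 50% or more above baseline.

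Add a listing of these patients and reconcile it with the renal AESI flags in both directions: rises without a flag, and flags without a rise.

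The cost is SAP wording, one table and one listing from central-laboratory data already collected. The table will include some unconfirmed rises and some outside normal hydration, and clinical significance is not a laboratory variable. A footnote should say so and cite Protocol Section 10.2.2. The categories are taken from the protocol, and no clinical threshold is changed.
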